2 ELIGIBILITY ASSESSMENT AND ENROLLMENT

2.1 ELIGIBILITY CRITERIA

2.1.1 Inclusion Criteria

- 2.1.1.1 A documented deleterious germline BRCA1/2 mutation (gBRCA1/2m) obtained in a CLIA-certified laboratory, including but not limited to Myriad Genetics, either by multi-gene panels or individual testing, for Cohort 1 participants prior to study enrollment. Participants with documented somatic BRCA mutation obtained in a CLIA-certified laboratory also will be considered for Cohort 1. Variants of uncertain significance (VUS) of BRCA1/2 are not considered deleterious. Participants with VUS or deleterious mutation in other genes without BRCA mutation can be considered for Cohort 2 or 3 or 5.
- 2.1.1.2 Participants enrolling in the sporadic high grade serous epithelial or high grade endometrioid ovarian cancer group, Cohort 2, must have a negative family history of hereditary breast ovarian cancer (HBOC) syndrome, or negative BRCA1/2 mutation test.
- 2.1.1.3 Participants enrolling in the triple negative breast cancer (ER-/PR-/Her2-) group, Cohort 3, must have a negative family history of HBOC syndrome, or negative BRCA1/2 mutation test. A family history of HBOC is defined by NCCN Genetic/Familial High-Risk Assessment: Breast and Ovarian guideline ([Appendix D](#))
- 2.1.1.4 For Cohorts 1-3, 5 and 6: participants must have breast and/or epithelial or endometrioid ovarian cancer, primary peritoneal cancer, and/or fallopian tube cancer histologically or cytologically confirmed at the NCI that is metastatic or unresectable and for which standard curative measures do not exist or are no longer effective. ER/PR/HER2 status needs to be documented either by an outside source or at NCI. Participants with BRCA1/2 mutation with history of or active breast and ovarian cancers are considered for Cohort 1. Those without gBRCA1/2m or somatic BRCA mutation will follow Exclusion Criteria [2.1.2.10](#).
- 2.1.1.5 Participants enrolling in Cohort 5, the recurrent platinum-resistant sporadic high grade serous epithelial or high grade endometrioid ovarian cancer group, must have a negative family history of HBOC syndrome, or negative BRCA1/2 mutation test. Participants should have recurrent platinum-resistant - defined as disease recurrence by imaging within 6 months of the last receipt of platinum-based chemotherapy. Rising CA125 only is not considered as platinum-resistant disease. Participants with primary platinum refractory disease defined as progression during or within 3 months after receiving first-line platinum based chemotherapy are not eligible.
- 2.1.1.6 All participants must have measurable disease, defined as at least one lesion that can be accurately measured in at least one dimension (longest diameter to be recorded for non-nodal lesions and short axis for nodal lesions) as ≥ 20 mm with conventional techniques or as ≥ 10 mm with spiral CT scan. See Section [6.2](#) for the evaluation of measurable disease.

CC Protocol #: 14-C-0156

Abbreviated Title: LY Chk1/2 Inhibitor

Amendment Version Date: 12/02/2020

- 2.1.1.7 All participants except Cohort 6 must have at least one lesion deemed safe to biopsy and be willing to undergo a mandatory baseline biopsy. For Cohort 5, the second biopsy at progression is mandatory for the responders (PR/CR/SD) \geq 4 months.
- 2.1.1.8 Participants enrolling in Cohort 6, the recurrent platinum-resistant sporadic high grade serous epithelial or high grade endometrioid ovarian cancer group, must have a negative family history of HBOC syndrome, or negative BRCA1/2 mutation test. Participants should have recurrent platinum-resistant, defined as disease recurrence by imaging within 6 months of the *last* receipt of platinum-based chemotherapy. This cohort should have measurable (defined by RECIST v1.1) but without biopsiable disease, determined by PI and Interventional Radiology (e.g., cystic abnormal mass, not safely biopsiable disease). Rising CA125 only is not considered as platinum-resistant disease. Participants with primary platinum refractory disease defined as progression during or within 3 months after receiving *first-line* platinum based chemotherapy are not eligible.
- 2.1.1.9 Participants must be at least 4 weeks from previous therapy (chemotherapy, hormonal therapy, and radiation therapy, or investigational agents; 6 weeks for mitomycin C).
- 2.1.1.10 The use of raloxifene, denosumab, or bisphosphonates for bone health is allowed.
- 2.1.1.11 There is no limit on the number of prior therapies.
- 2.1.1.12 Participants must be at least 1 week from the last dose of complementary or alternative medications.
- 2.1.1.13 Participants who have had major surgery must be fully recovered and \geq 4 weeks post-operative prior to enrolling on study.
- 2.1.1.14 Age \geq 18 years.
- 2.1.1.15 ECOG performance status \leq 2.
- 2.1.1.16 Participants must have normal organ and marrow function (in the absence of transfusion 24 hours prior to dosing) as defined below:
 - leukocytes \geq 3,000/mcL
 - absolute neutrophil count \geq 1,500/mcL
 - platelets \geq 100,000/mcL
 - hemoglobin \geq 10mg/dL
 - total bilirubin \leq 1.5 X institutional upper limit of normal
 - AST(SGOT)/ALT(SGPT) \leq 3 X institutional upper limit of normal
 - creatinine \leq 1.5 X institutional upper limit of normal
 - OR
 - measured creatinine clearance \geq 45 mL/min/1.73 m² for participants with creatinine levels above institutional normal.
- 2.1.1.17 Potassium (K) should be within the range of \geq 3.6 mEq/L.
- 2.1.1.18 Women of childbearing potential must have a negative urine or serum pregnancy test within 7 days prior to the start of the study.
- 2.1.1.19 The effects of LY2606368 on the developing human fetus are unknown. For this reason, all subjects of reproductive potential must agree to use adequate contraception

CC Protocol #: 14-C-0156

Abbreviated Title: LY Chk1/2 Inhibitor

Amendment Version Date: 12/02/2020

prior to study entry, for the duration of study participation, and for at least four months following the last dose of experimental therapy. All subjects of reproductive potential must also agree to use both a barrier method and a second method of birth control during the course of the study and for four months after the last dose of study drug(s). Should a woman become pregnant or suspect she is pregnant while she is participating in this study, she should inform her treating physician immediately.

2.1.1.20 Ability of subject to understand, adhere to protocol requirements and the willingness to sign a written informed consent document.

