⁷Groups 1-3, 5 and 6: Performed every 2 cycles (+/- 7 days), beginning with Cycle 3 Day 1, prior to drug administration. For participants who have been on study \geq 4 years, CT scans will be performed every 3 cycles (+/-7 days). MRI may be used as clinically indicated for participants who cannot tolerate CT contrast.

⁸ECGs will be performed at screening/baseline, before (anytime prior to Prexasertib infusion start) and at the end of each infusion (within 30min +/-20min), C1D15, C2D1, C3D1, and then every 3 months (+/- 2 weeks) and post treatment. Baseline/screening EKG may be used as C1D1 pre-infusion EKG if done within one week.

⁹In women of childbearing potential

¹⁰As indicated in section **12.3**, all subjects \geq age 18 will be offered the opportunity to complete an NIH advanced directives form. This should be done preferably at baseline but can be done at any time during the study as long as the capacity to do so is retained. The completion of the form is strongly recommended, but is not required.

CC Protocol #: 14-C-0156

Abbreviated Title: LY Chk1/2 Inhibitor

Amendment Version Date: 12/02/2020

¹¹End of treatment visit will occur approximately 30 days after the last dose of study drug. If the participant cannot return to the Clinical Center for this visit, a request will be made to collect required clinical labs (specify as needed) from a local physician or laboratory. If this is not possible, participants may be assessed by telephone for symptoms.

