6.3.1 Definitions

Evaluable for toxicity: All participants will be evaluable for toxicity from the time of their first treatment with LY2606368.

Evaluable for objective response: Only those participants who have measurable disease present at baseline, have received at least one cycle of therapy, and have had their disease re-evaluated will be considered evaluable for response. These participants will have their response classified according to the definitions stated below. (Note: Participants who exhibit objective disease progression prior to the end of cycle 1 will also be considered evaluable.)

Evaluable Non-Target Disease Response: Participants who have lesions present at baseline that are evaluable but do not meet the definitions of measurable disease, have received at least one cycle of therapy, and have had their disease re-evaluated will be considered evaluable for non-target disease. The response assessment is based on the presence, absence, or unequivocal progression of the lesions.

CC Protocol #: 14-C-0156
Abbreviated Title: LY Chk1/2 Inhibitor
Amendment Version Date: 12/02/2020

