6.3.2 Disease Parameters

Measurable disease: Measurable lesions are defined as those that can be accurately measured in at least one dimension (longest diameter to be recorded) as:

- By chest x-ray: ≥ 20 mm;
- By CT scan:
 - Scan slice thickness 5 mm or under: as ≥ 10 mm
 - Scan slice thickness >5 mm: double the slice thickness
- With calipers on clinical exam: ≥ 10 mm.

All tumor measurements must be recorded in millimeters (or decimal fractions of centimeters).

Malignant lymph nodes. To be considered pathologically enlarged and measurable, a lymph node must be ≥ 15 mm in short axis when assessed by CT scan (CT scan slice thickness recommended to be no greater than 5 mm). At baseline and in follow-up, only the short axis will be measured and followed.

Non-measurable disease. All other lesions (or sites of disease), including small lesions (longest diameter <10 mm or pathological lymph nodes with ≥ 10 to <15 mm short axis), are considered non-measurable disease. Bone lesions, leptomeningeal disease, ascites, pleural/pericardial effusions, lymphangitis cutis/pulmonitis, inflammatory breast disease, and abdominal masses (not followed by CT or MRI), are considered as non-measurable.

Note: Cystic lesions that meet the criteria for radiographically defined simple cysts should not be considered as malignant lesions (neither measurable nor non-measurable) since they are, by definition, simple cysts.

‘Cystic lesions’ thought to represent cystic metastases can be considered as measurable lesions, if they meet the definition of measurability described above. However, if non-cystic lesions are present in the same participant, these are preferred for selection as target lesions.

Target lesions. All measurable lesions up to a maximum of 2 lesions per organ and 5 lesions in total, representative of all involved organs, should be identified as **target lesions** and recorded and measured at baseline. Target lesions should be selected on the basis of their size (lesions with the longest diameter), be representative of all involved organs, but in addition should be those that lend

CC Protocol #: 14-C-0156

Abbreviated Title: LY Chk1/2 Inhibitor

Amendment Version Date: 12/02/2020

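### Criterion 2.1.1.6 admits participants whose only disease is nodes of 10 to <15 mm on CT, but 6.3.2 and 6.3.1 make them non-evaluable for the primary endpoint

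*Combined protocol and SAP*

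**What the plan says.** - **Eligibility (2.1.1.6, all participants).** The criterion carries its own definition of measurable disease. It names the short axis for nodes and applies the same limits as for other lesions: "short axis for nodal lesions) as ≥ 20 mm with conventional techniques or as ≥ 10 mm with spiral CT scan". It then sends the reader to Section 6.2, which is the Data Sharing Plan.
- **Response assessment (6.3.2).** To be measurable, "a lymph node must be ≥ 15 mm in short axis when assessed by CT scan". The non-measurable category expressly includes "pathological lymph nodes with ≥ 10 to <15 mm short axis".
- **Evaluability (6.3.1).** The objective-response population is restricted: "Only those participants who have measurable disease present at baseline, have received at least one cycle of therapy", and re-evaluation is also required. A note adds an exception: "Participants who exhibit objective disease progression prior to the end of cycle 1 will also be considered evaluable". A separate non-target category takes in "Participants who have lesions present at baseline that are evaluable but do not meet the definitions of measurable disease".
- **Biopsy (2.1.1.7).** Everyone outside Cohort 6 needs "at least one lesion deemed safe to biopsy and be willing to undergo a mandatory baseline biopsy". The criterion sets no size or measurability condition for that lesion.
- **Imaging (3.4, footnote 7).** Scheduled CT on treatment is every two cycles, "beginning with Cycle 3 Day 1, prior to drug administration". Section 3.2 allows earlier imaging when there are signs or symptoms of clinical progression.
- **Cohort 6 (2.1.1.8).** This cohort has its own requirement, disease measurable by RECIST v1.1.

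**The concern.** The same node, measured on the same axis by the same modality, is measurable at entry and non-measurable at response assessment. Objective response rate is the primary objective (1.1.1). A participant admitted on the wider definition undergoes a mandatory biopsy and treatment and then, in general, falls outside the population that answers the primary question. Because cohort sizes are set in evaluable participants, each such case also has to be replaced within the accrual ceiling.

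**Working it through.** **1. Where the two definitions part.** Spiral CT, nodal short axis; 2.1.1.6 requires at least 10 mm, 6.3.2 at least 15 mm:

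| Short axis (mm) | Measurable under 2.1.1.6 | Measurable under 6.3.2 |
|---|---|---|
| 9 | no | no |
| 10 | yes | no |
| 12 | yes | no |
| 14.9 | yes | no |
| 15 | yes | yes |
| 20 | yes | yes |

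The conflict covers exactly 10 to <15 mm.

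**2. Who is caught.** Only participants in Cohorts 1-3 and 5 whose sole qualifying disease is CT-measured nodes in that range.
- Anyone with another measurable lesion is unaffected.
- Cohort 6 is largely protected by 2.1.1.8, and Cohort 4 is closed.
- Palpable nodes are left out of the claim, because 6.3.3 lists them among superficial lesions measurable by calipers from 10 mm.
- No other criterion sets a 15 mm nodal minimum for these cohorts.

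**3. What happens to them.** They meet 2.1.1.6. If the other criteria are met they are biopsied under 2.1.1.7 and treated. Under 6.3.1 they lack measurable baseline disease, so they are evaluable for objective response only through the early-progression note. With 28-day cycles the first scheduled scan comes after two cycles, later than the end of cycle 1. The note therefore depends on progression being documented outside the scheduled scans.

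**4. Effect on the sample size.** Inputs are from Section 10: 24 in each of Cohorts 1-3, 36 in Cohort 5, 35 in Cohort 6, total 143 evaluable, ceiling 153.
- 24 + 24 + 24 + 36 + 35 = 143, which reproduces the stated total. The sum treats each 24 as evaluable participants.
- Nominal allowance for non-evaluable participants: 153 - 143 = 10.
- If c Cohort 4 participants count towards the ceiling, the allowance is 10 - c. The documents give neither c nor the counting rule.
- Each affected participant uses one place.

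**5. Design figures.** These are defined on evaluable participants and do not move. On recalculation:
- Cohorts 1-3: probability of early termination 0.95^9 = 0.630 (stated 63.0%), alpha 0.093, power 0.903.
- Cohort 5 at 13 or more of 36: power 0.893 (stated 89%).
- Cohort 6 at 11 or more of 35: power 0.888 (stated 88%).

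**The case against.** The best reply is that RECIST 1.1 governs in practice. Section 6.3 adopts it for response and progression. The pointer in 2.1.1.6 looks like part of a numbering shift, since 3.2 cites 6.2.4 for complete-response guidance and 6.1 cites 6.3 for toxicity, so it was probably meant to lead to the present 6.3. High-grade serous ovarian scans also have two-reader central review under RECIST 1.1 (7.4.2). This makes it less likely that 2.1.1.6 is applied in isolation, but it does not remove the conflict. Redirected to 6.3.2, the pointer would contradict the criterion's own number. The central review is an exploratory objective (1.1.3), is not given a role in eligibility, and does not cover breast cancer participants.

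It is also fair to say that these participants are not lost to the study. They count for toxicity, their biopsies and blood serve the biomarker objectives, and a complete response can be recorded in the non-target table. That stands, although 6.3.1 keeps the non-target category apart from objective response.

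A reader might go further in three ways that the documents do not support:
- **That the allowance could be exhausted at some calculable share of node-only cases.** Any such break-even needs the number of other non-evaluable participants and the Cohort 4 count. The interim data in 1.2 show 20 of 25 evaluable in Cohort 2 and 6 of 7 in Cohort 1, so other non-evaluable cases cannot be assumed to be nil. Some of those six may only have been awaiting assessment.
- **That the early-progression exception will almost never apply.** No frequency is given, and 3.2 permits earlier scans.
- **That response rates will be inflated by small nodes chosen as targets.** Section 6.3.2 governs target lesions and excludes those nodes.

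**Conclusion.** The plan is inconsistent as written. Followed literally, it can enrol, biopsy and treat participants in Cohorts 1-3 and 5 who generally cannot inform the primary endpoint. This rests on reading 2.1.1.6 by its own stated threshold, and it is limited to node-only disease of 10 to <15 mm on CT. The documents give no count; the number is probably small. The main cost falls on the affected participants. For the trial, the cost is one place per case from a nominal 10, fewer if Cohort 4 enrolees count under the 153. It would be wrong to infer that a stated sample size, error rate or power is in error. The correction is worth making because it is inexpensive and bears on who can answer the primary question.

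**What to change.** - Replace the size wording in 2.1.1.6 with a reference to the measurable-disease definition in 6.3.2/6.3.3, and correct the cross-reference from 6.2 to those sections. The stale pointers in 3.2 and 6.1 can be corrected at the same time.
- State whether a palpable node of 10 to <15 mm is measurable, since 6.3.2 and 6.3.3 can be read differently.
- If participants with only such nodes are already enrolled, identify them and apply 6.3.1 consistently in the response analysis.

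**Cost.** A protocol amendment with IRB approval. Eligibility narrows slightly: node-only disease of 10 to <15 mm on CT no longer qualifies, nor do lesions smaller than twice the slice thickness when slices exceed 5 mm. Whether eligibility also widens for caliper-measured lesions depends on what 2.1.1.6 means by conventional techniques, a term the documents do not define. No stated sample size, alpha or power changes.

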2.1.2 Exclusion Criteria

2.1.2.1 Participants who are receiving any other investigational agents.

2.1.2.2 Participants with known brain metastases should be excluded from this clinical trial because of their poor prognosis and because they often develop progressive neurologic dysfunction that would confound the evaluation of neurologic and other adverse events. Participants with brain metastases diagnosed greater than 1 year prior to study entry may be considered if they received sterilizing therapy to the CNS (resection or radiation) and have been CNS recurrence-free for the 1-year period.

2.1.2.3 Participants who have had prior treatment with LY2606368 or other Chk inhibitors

2.1.2.4 Participants with a serious cardiac condition, such as congestive heart failure; New York Heart Association Class III/IV heart disease; unstable angina pectoris; myocardial infarction within the last 3 months; valvulopathy that is severe, moderate, or deemed clinically significant despite medical intervention; or arrhythmias that are symptomatic or refractory to medical intervention.

2.1.2.5 Participants who have QTc interval of > 470 msec on a screening electrocardiogram.

2.1.2.6 Participants with a prior history of drug-induced serotonin syndrome, or a family history of long-QT syndrome.

2.1.2.7 Lack of recovery of prior adverse events due to prior cancer therapy to Grade ≤ 1 (NCI CTCAE; except alopecia). Electrolyte abnormalities that are corrected with supplementation will be eligible. Participants with platinum-related grade 2 or greater hypomagnesemia (on replacement) will be eligible. Stable persistent grade 2 peripheral neuropathy may be allowed as determined on a case-by-case basis at the discretion of the PI.

2.1.2.8 Uncontrolled intercurrent illness including, but not limited to, symptomatic congestive heart failure, unstable angina pectoris, cardiac arrhythmia, clinically significant GI bleeding or hemoptysis within 28 days prior to the start of the study, or psychiatric illness/social situations that would limit compliance with study requirements.

2.1.2.9 Participants with active infection will not be eligible, but may become eligible once infection has resolved and they are at least 7 days from completion of antibiotics.

2.1.2.10 Another previous or current invasive malignancy within the last 2 years, with the exception of curatively treated stage Ia cervical carcinoma, or resected stage Ia endometrial cancer, and noninvasive nonmelanoma skin cancers. Participants with

CC Protocol #: 14-C-0156

Abbreviated Title: LY Chk1/2 Inhibitor

Amendment Version Date: 12/02/2020

gBRCA1/2m and primary breast or ovarian cancers will be eligible for Cohort 1 (2.1.1.4).

2.1.2.11 HIV-positive participants on combination antiretroviral therapy are ineligible because of the potential for pharmacokinetic interactions with LY2606368. HIV- positive participants who are not on HAART and have CD4 counts > 500 will be considered on an individual basis.

2.2 PARTICIPANT REGISTRATION AND STATUS UPDATE PROCEDURES

Registration and status updates (e.g., when a participant is taken off protocol therapy and when a participant is taken off-study) will take place per CCR SOP ADCR-2, CCR Participant Registration & Status Updates found [here](#).

2.3 TREATMENT ASSIGNMENT AND RANDOMIZATION/STRATIFICATION PROCEDURES

Cohorts

Number	Name	Description
1	BRCA mutation positive breast or ovarian cancer	Breast or ovarian cancer patients with a documented deleterious germline BRCA mutation (gBRCAm) or somatic BRCA mutation.
2	BRCA mutation negative ovarian cancer	High-grade serous ovarian cancer (HGSOC) patients with negative BRCA mutation testing or negative family history of hereditary breast and ovarian cancer syndrome
3	BRCA mutation negative triple negative breast cancer	Triple negative breast cancer patients with negative BRCA mutation testing or negative family history of hereditary breast and ovarian cancer syndrome
4	Prostate cancer	Effective with amendment I (version date 4/24/2017), metastatic castration-resistant prostate cancer cohort is closed.
5	BRCA mutation negative ovarian cancer, biopsy	High-grade serous ovarian cancer (HGSOC) patients with negative BRCA mutation testing or negative family history of hereditary breast and ovarian cancer syndrome, they must have recurrent platinum-resistant HGSOC with measurable and biopsiable disease.
6	BRCA mutation negative ovarian cancer, non-biopsy	High-grade serous ovarian cancer (HGSOC) patients with negative BRCA mutation testing or negative family history of hereditary breast and ovarian cancer syndrome, they must have platinum-resistant HGSOC with measurable but without biopsiable disease.

Arms

Number	Name	Description
1	Prexasertib	Prexasertib monotherapy treatment

Randomization/Stratification and Arm Assignment

Randomization procedures do not apply to this trial.

No stratification is planned for this study.

Participants in all Cohorts will be directly assigned to Arm 1.

